1.1. RAP Amendment

Revision chronology:

RAP Section	Amendment Details
Reporting and Analysis Plan_212482_Final	
Reporting and Analysis Plan_212482_Amendment	
The primary reason for this RAP amendment is to include reporting and analysis details for newly added cohorts 4b and 4h to align with the latest protocol amendment 6.	
RAP Section	Amendment Details
Section 2.2 Study Objectives and Estimands Section 3.3 Study Design Section 3 Planned Analyses	
 • Updated objectives, endpoints, study schematic, study design features and planned analyses, as described protocol amendment 6.
Section 3.2 Interim Analysis	
 • Updated description of interim analyses to align with protocol amendment 6 • Added decision to conduct an unblinded preliminary interim analysis for Cohort 1-5
Section 4 Analysis Populations	
 • Added analysis population details for the cohort 1-5 preliminary interim analysis: data displays will exclude cohort 4b data from participants who have received injection 1 but have not yet completed Injection 2 Day 1 or Follow-up Week 4; Cohort 4b will remain

	blinded to randomized CCI [REDACTED] [REDACTED] • Added Safety – LA Exposed population
Section 5.1 Study Treatment & Sub-group Displays Descriptors	• Added treatment groups for cohort 4b and cohort 4h and shorted treatment descriptors for all cohorts. • Update the list of PK pairwise between cohorts and cross study historical comparisons to be evaluated in statistical analyses.
Section 7.1 Adverse Events Analyses	• Added details for Cohort 4b: adverse event data will be summarized by injection CCI [REDACTED] [REDACTED]
Section 7.4 Other Safety/Exploratory Analyses	• CCI [REDACTED] [REDACTED] [REDACTED] [REDACTED]
Section 7.5 Exploratory Crossover Analysis for Cohort 4b	• CCI [REDACTED] [REDACTED]
Section 8.1.1.2 Derived Pharmacokinetic Parameters	• Added dose normalized PK parameters for Cohort 3 injection 1 (footnoted) • Added PK parameters for Cohort 4b and 4h • Added C4 & AUC (0-4) PK parameters for Cohort 5
Section 8.1.5 Statistical Analyses/Methods	• Added additional Cohort 4b summary of PK concentrations and parameters by treatment sequence and period CCI [REDACTED] [REDACTED] [REDACTED]

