				Inj.1 400 mg IM Gluteal	39
				Inj.2 100 mg SC Abdomen	40
				Follow-up	41
				Overall ¹	42
	C4b CAB 400 + Topical Steroid or NSAID 4	A4bG1	CAB 400 mg/mL Injections 4- weeks apart in CCI	Oral CAB 30 mg QD	43
				CCI	44
				CCI	45
				Follow-up	46
				Overall ¹	47
	C4b CAB 400 + Topical Steroid or NSAID 4	A4bG2	CAB 400 mg/mL Injections 4- weeks apart in CCI	Oral CAB 30 mg QD	4833
				CCI	49
				CCI	50
				Follow-up	51
				Overall ¹	52
		A4h		Oral CAB 30 mg QD	53

	C4h CAB 400 + rHUPH20		CAB 400 mg/mL Injection in the abdomen with rHuPH20	Inj. 1 CAB 400 mg + 5000 U rHUPH20 SC Abdomen	54
				Follow-up	55
				Overall ¹	56
	C4h CAB 200 + rHUPH20	A4h	CAB 200 mg/mL Injection in the abdomen with rHuPH20	Oral CAB 30 mg QD	57
				Inj. 1 CAB 400 mg + 5000 U rHUPH20 SC Abdomen	58
				Follow-up	59
				Overall ¹	60
	N/A	N/A	Pooled Group ²	Pooled Oral CAB 30 mg QD OLI ONLY	61
				Pooled Oral CAB 30 mg QD	62
				Pooled CAB 400 mg/mL Q4W 400 mg IM Gluteal	63
				Pooled CAB 200 mg/mL Q4W 400 mg IM Gluteal	64
				Pooled CAB 400 mg/mL Q4W 200 mg SC	65
				Pooled CAB 200 mg/mL Q4W 100 mg SC	66
				Pooled CAB 400 mg/mL Q4W 400 mg Lateral Thigh	67
				Pooled CAB 200 mg/mL Q4W 400 mg Lateral Thigh	68
Part 2	C5 CAB 400 ³	A5	CAB 400 mg/mL IM injections 12-weeks apart in gluteus muscle (cohort 5)	Oral CAB 30 mg QD	69
				Inj. 1 800 mg IM Gluteal	70
				Follow-up	71
				Overall ¹	72
	C5 CAB 200	C5	CAB 200 mg/mL IM injections 12-weeks apart in gluteus muscle (cohort 5)	Oral CAB 30 mg QD	73
				Inj. 1 400 mg IM Gluteal	74
				Follow-up	75
				Overall ¹	76
	N/A	N/A	Historical Data, CAB 200 mg/mL	(ATLAS/FLAIR) Inj. 1 CAB 600 mg IM Gluteal ³	77
				(ATLAS/FLAIR) Inj. 2 CAB 400 mg IM Gluteal ³	78
				(ÉCLAIR) Inj. 1 CAB 800 mg IM Gluteal ³	79

Note: A1 = Active Drug in Cohort 1; A2 = Active Drug in Cohort 2; A3 = Active Drug in Cohort 3; A4 = Active Drug in Cohort 4; A4h = Active Drug in Cohort 4h; A5 = Active Drug in Cohort 5; A6 = Active Drug in Cohort 6; C1 = Cohort 1, C2 = Cohort 2, C3 = Cohort 3, C4 = Cohort 4, C4b = Cohort 4b, C4h = Cohort 4h, C5 = Cohort 5.

1. Overall group is not applicable for PK analyses.
2. Pooled active and AC groups are only applicable when there is more than one cohort at the stated dose (mg) to combine for the specific summary.
3. Historical data for formulation of 200 mg/mL from the Phase 3 program, only applicable for PK analyses.

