Treatment comparisons for the PK pairwise and cross study historical comparison (See Section 8.1.5) will be displayed by injection using the following descriptors:

Pairwise Comparisons for AUC(0- τ), C_{max}, and C _{τ} :

Injection 1 (CAB 400 mg/mL):

1. C2 CAB400 - Inj. 1 600 mg SC Abdomen vs C1 CAB400 - Inj. 1 600 mg IM Gluteal
2. C3 CAB400 - Inj. 1 600 mg IM Lateral Thigh vs C1 CAB400 - Inj. 1 600 mg IM Gluteal
3. C2 CAB400 - Inj. 1 600 mg SC Abdomen vs C3 CAB400 - Inj. 1 600 mg IM Lateral Thigh
4. C4h CAB400 + rHUPH20 - Inj. 1 CAB 400 mg + 5000 U rHUPH20 SC Abdomen vs C4 CAB400 - Inj. 1 400 mg IM Gluteal

Injection 2 (CAB 400 mg/mL):

1. C3 CAB400 - Inj. 2 400 mg IM Lateral Thigh [participants who received 600 mg for Injection 1] vs C1 CAB400 - Inj. 2 400 mg IM Gluteal

Historical Comparisons:

Injection 1 (CAB 400 mg/mL):

1. C1 CAB400 - Inj. 1 600 mg IM Gluteal vs Week 4 post injection 1 in ATLAS/FLAIR IM Gluteal CAB 600 mg (CAB 200 mg/mL) Q4W
2. C2 CAB400 - Inj. 1 600 mg SC Abdomen vs Week 4 post injection 1 in ATLAS/FLAIR IM Gluteal CAB 600 mg (CAB 200 mg/mL) Q4W
3. C3 CAB400 - Inj. 1 600 mg IM Lateral Thigh vs Week 4 post injection 1 in ATLAS/FLAIR IM Gluteal CAB 600 mg (CAB 200 mg/mL) Q4W
4. C4 CAB400 - Inj. 1 400 mg IM Gluteal vs Week 4 post injection 1 in ATLAS/FLAIR IM Gluteal CAB 600 mg (CAB 200 mg/mL) Q4W [dose normalize to 400 mg]

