5. CCI [REDACTED]
6. C4h CAB400 + rHUPH20 - Inj. 1 CAB 400 mg + 5000 U rHUPH20 SC Abdomen vs Week 4 post injection 1 in ATLAS/FLAIR IM Gluteal CAB 600 mg (CAB 200 mg/mL) Q4W [dose normalize to 400 mg]
7. C4h CAB200 + rHUPH20 - Inj. 1 CAB 400 mg + 5000 U rHUPH20 SC Abdomen vs Week 4 post injection 1 in ATLAS/FLAIR IM Gluteal CAB 600 mg (CAB 200 mg/mL) Q4W [dose normalize to 400 mg]

8. C5 IM Gluteal CAB 800 mg (CAB 400 mg/mL) Q12W Week 12 post injection 1 vs Week 4 post injection 1 in ATLAS/FLAIR IM Gluteal CAB 600 mg (CAB 200 mg/mL) Q4W [dose normalize to 800 mg]
9. C5 IM Gluteal CAB 800 mg (CAB 400 mg/mL) Q12W Week 12 post injection 1 vs Week 12 post injection 1 in ÉCLAIR IM Gluteal CAB 800 mg (CAB 200 mg/mL) Q12W
10. C5 IM Gluteal CAB 800 mg (CAB 400 mg/mL) Q12W Week 12 post injection 1 [Male participants only] vs Week 12 post injection 1 in ÉCLAIR IM Gluteal CAB 800 mg (CAB 200 mg/mL) Q12W

Injection 2 (CAB 400 mg/mL):

1. C1 CAB400 - Inj. 2 400 mg IM Gluteal vs Week 4 post injection 2 in ATLAS/FLAIR IM Gluteal CAB 400 mg (CAB 200 mg/mL) Q4W
2. C2 CAB400 - Inj. 2 200 mg SC Abdomen vs Week 4 post injection 2 in ATLAS/FLAIR IM Gluteal CAB 400 mg (CAB 200 mg/mL) Q4W [dose normalize to 200 mg]
3. C3 CAB400 - Inj. 2 400 mg IM Lateral Thigh vs Week 4 post injection 2 in ATLAS/FLAIR IM Gluteal CAB 400 mg (CAB 200 mg/mL) Q4W

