C _τ	Trough concentrations (C _τ) Tau=24 hours for OLI Day 29 Tau is 4 weeks for Inj. Phase in Cohort 1-4, 4b, and 4h Tau is 12 weeks for Inj. Phase in cohort 5.	Day 29	For Injection 1 & 2 in Part 1 and Part 2
C _τ /D	Trough concentrations (C _τ)/Dose Tau=24 hours for OLI Day 29 Tau is 4 weeks for Inj. Phase in Cohort 1-4, 4b, and 4h Tau is 12 weeks for Inj. Phase in cohort 5.	Day 29	For Injection 1 & 2 in Part 1 and Part 2
C4 Cohort 5 only	Trough concentrations on Week 4	NA	For Injection 1 & 2 in Part 2
C24	Trough Concentrations on Day 2 (24 hour)	Day 1	
t _{1/2}	Terminal absorption elimination half-life will be calculated as: t _{1/2} = ln2 / KALA	NA	For Injection 1 (Cohort 4h) & 2 in Part 1 and Part 2.
KALA	Terminal absorption elimination rate constant, Long-acting	NA	For Injection 1 (Cohort 4h) & 2 in Part 1 and Part 2

NOTES:

- Additional parameters may be included as required.
- In addition to the PK parameters calculated based on the observed concentrations for the 2 participants from Cohort 3 who received a CAB400 - Inj. 1 400 mg IM Lateral Thigh. PK parameters adjusted to a 600 mg dose will be calculated for these participants as well. The adjustment will be performed using a 50% increase of the plasma PK parameters.

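### The Cohort 3 Injection 2 historical comparison lacks the 600 mg-first limit that its pairwise counterpart carries, which leaves a small expected downward bias in the trough ratio

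*SAP*

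**What the plan says.** - **Pairwise, Injection 2, item 1 (SAP 5.1):** "C3 CAB400 - Inj. 2 400 mg IM Lateral Thigh [participants who received 600 mg for Injection 1] vs C1 CAB400". Cohort 3 is limited by first dose.
- **Historical, Injection 2, item 3 (SAP 5.1):** "C3 CAB400 - Inj. 2 400 mg IM Lateral Thigh vs Week 4 post injection 2 in ATLAS/FLAIR". There is no first-dose limit and no dose-normalisation tag.
- **Reference:** the treatment table in SAP 5.1 gives ATLAS/FLAIR as 600 mg at Injection 1 and 400 mg at Injection 2.
- **Who differs:** the notes to SAP 8.1.1.2 refer to the "2 participants from Cohort 3 who received a CAB400 - Inj. 1 400 mg IM Lateral Thigh". For them, parameters adjusted to 600 mg are calculated in addition to the observed ones: "The adjustment will be performed using a 50% increase of the plasma PK parameters". The note does not name the injection. The SAP's own change log in 1.1 does: "Added dose normalized PK parameters for Cohort 3 injection 1 (footnoted").
- **Display groups:** the treatment table splits Cohort 3 Injection 1 into 600 mg and 400 mg rows, but has a single Injection 2 row.
- **Elsewhere:** SAP 8.1.5.1 refers back to 5.1 for the comparisons. The PK population in SAP 4 and Table 3.6 in SAP 10.10.7 add no restriction. Protocol 10.4.2 names Cohort 3 among the cohorts for the Week 8 historical comparison, without a first-dose condition.

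**The concern.** The trough four weeks after Injection 2 contains drug from both injections. A participant who had 400 mg first is expected to have a lower Week 8 trough than one who had 600 mg first, whatever the route or formulation. The bracket in the pairwise item shows that the SAP already treats the first dose as relevant to this injection. The same reasoning applies to a reference in which everyone had 600 mg first.

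The ratio of trough to historical data is a primary endpoint. Without the limit, the lateral-thigh ratio carries a component that comes from the loading dose, and a reader setting the pairwise and historical results side by side would not know that the sets may differ. The 50% adjustment does not solve this. Both subgroups had 400 mg as the second dose, so multiplying a whole Injection 2 trough by 1.5 would over-correct.

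**Working it through.** **Inputs**
- Geometric mean troughs assumed in protocol Table 3: 1.3898 at Week 4 (after 600 mg) and 1.8446 at Week 8 (after 600 mg then 400 mg).
- SD of log concentration at Week 8: 0.47376. Planned sizes: 15 against 577 (protocol Table 4).
- Cohort 3: 18 active, with at least 15 evaluable intended. Two had 400 mg first.

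**1. Reproduce the plan's precision.** Half-width = t(0.95; n1 + n2 - 2) × SD × √(1/n1 + 1/n2). With 15 and 577 this gives 0.20412, against 0.20413 in Table 4, and an interval of 0.8154 to 1.2265 at a ratio of 1.0, as stated there.

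**2. Share of the Week 8 trough from Injection 1 (f).** The documents do not give f. Under dose proportionality and superposition, Table 3 implies:
- contribution of a 400 mg second dose: 1.3898 × 400/600 = 0.9265
- carry-over: 1.8446 - 0.9265 = 0.9181
- f = 0.9181/1.8446 = 0.498

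**3. Expected trough after 400 mg then 400 mg.** 0.9265 + 0.9181 × 2/3 = 1.5386. Relative to the reference, r = 1.5386/1.8446 = 0.834. In general r = 1 - f/3.

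**4. Effect on the geometric mean ratio.** Two of n participants multiply it by r^(2/n).

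| f | r | n = 15 | n = 18 |
|---|---|---|---|
| 0.10 | 0.967 | 0.9955 | 0.9962 |
| 0.25 | 0.917 | 0.9885 | 0.9904 |
| 0.498 | 0.834 | 0.9761 | 0.9800 |
| 0.75 | 0.750 | 0.9624 | 0.9685 |
| 1.00 | 0.667 | 0.9474 | 0.9559 |

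At f = 0.498 the shift is 2.4% (n = 15) or 2.0% (n = 18), which is 11-12% of the 90% half-width. At the limit f = 1 it is 24-27% of the half-width.

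**5. Can the direction be relied on?** The expected log difference for the two is ln 0.834 = -0.181. The standard error of the difference between two people and the other 13 is 0.47376 × √(1/2 + 1/13) = 0.360; with 16 others it is 0.355. The probability that the two raise the observed ratio is about 0.30-0.31.

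**6. Cost of restricting.** The log half-width goes from 0.204 (n = 15) to 0.219 (n = 13), 7.2% wider, or from 0.187 (n = 18) to 0.198 (n = 16), 5.9% wider. With the unequal-variance model of SAP 8.1.5.1, the same SD in both groups and Satterthwaite degrees of freedom, the widening is 8.5% and 6.7%.

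**7. Bias against precision.** Root mean squared error on the log scale at f = 0.498:
- n = 15: √(0.0242² + 0.1239²) = 0.126 with everyone; 0.133 restricted to 13.
- n = 18: √(0.0202² + 0.1134²) = 0.115 with everyone; 0.120 restricted to 16.

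Keeping everyone has the smaller error until f reaches about 0.90.

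**The case against.** Four arguments can be made for leaving item 3 alone.

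- **The pairwise list has its own rule.** SAP 8.1.5.1 confines pairwise contrasts to cohorts on the same dose by different routes, and the cross-study bullet has no such rule. This does not explain the bracket, since all of Cohort 3 had 400 mg at Injection 2. The bracket can only concern the first dose. The historical list also matches dose where needed, by normalising, and restricts by subgroup in one item.
- **Item 3 follows the protocol.** Protocol 10.4.2 asks for Cohort 3 as a whole, in an amendment dated after the Cohort 3 dose reduction, and SAP 2.1 declares no departure. This stands: replacing the full set would narrow a protocol-defined comparison.
- **Dropping two people costs more precision than the bias is worth.** This also stands on the figures above, unless carry-over is about 90% or more.
- **The effect is small and fragile.** The 50% share comes from pooled 200 mg/mL gluteal data and is applied to 400 mg/mL in the thigh under a proportionality that the SAP itself sets out to assess. The study tests no formal hypothesis. This limits the weight of the point but does not remove the mismatch.

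A reader might infer that the two participants do pull the ratio down, or that they must be excluded. The documents support neither. The direction is only an expectation for two people, and the documents do not say that both received Injection 2 or have an evaluable trough.

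**Conclusion.** The point holds as a minor inconsistency in how the Cohort 3 Injection 2 set is defined. Item 3 admits up to two 400/400 mg participants to a comparison whose reference is all 600/400 mg, and nothing in the SAP removes them or adjusts their Injection 2 trough.

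The expected downward bias is about 2.0-2.4% if half of the Week 8 trough is carry-over. The bounds of 0.4% and 5.3% correspond to carry-over shares of 10% and 100% at n = 15. These figures assume linear superposition, dose proportionality, and an evaluable Week 4 post-Injection 2 trough from both participants. At half carry-over the shift lies well inside the 90% interval, and no dose decision is shown to depend on it. The case is for showing the matched contrast alongside the full one, so that the reader can see whether the loading dose matters.

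**What to change.** 1. Under historical Injection 2 item 3, add a row for Cohort 3 with the same bracket as pairwise Injection 2 item 1. Report it next to the protocol-defined comparison of all Cohort 3, and state that the latter includes any 400/400 mg participants with an evaluable trough.
2. Split the Cohort 3 Injection 2 PK summary by first-injection dose, as Injection 1 already is.
3. State in SAP 8.1.1.2 that the 50% adjustment applies to Injection 1 parameters only.

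No further listing is needed: Listings 38 and 40 already give individual injection-phase concentrations and parameters.

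The cost is one extra table row, one split display group and one clarifying sentence. No new data are needed. The restricted row's 90% half-width is about 6-7% wider with the Table 4 formula (n = 13 to 16), and about 7-9% wider with the SAP's unequal-variance model. The full-cohort row keeps its present precision.

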10.4.2. Primary Endpoints

The primary endpoints are injection phase PK parameters including C_{max}, t_{max}, C_τ, AUC_{0-t}, terminal phase half-life(t_{1/2}) and absorption rate constant (K_A) for each cohort. The PK Parameter Population will be used for the analyses of these endpoints.

Following log_e-transformation, the PK parameters will be summarized by treatment and time period if applicable. Summary statistics (such as mean, standard deviation, median, min, max) will be produced for the log_e-transformed PK parameters. The Summary statistics will also be back-transformed to the original scale to produce geometric mean and between participant coefficient variation (CV_b).

In addition, the primary analyses will also include the following assessments based on geometric mean ratios:

- Pair-wise comparisons between Cohorts 1, 2, 3, 4, 4b, and 4h for CAB 400 mg/mL plasma trough concentrations (C_τ), C_{max} and AUC_{0-t} at Week 4 (Injection 1 Day 28) and Week 8 (Injection 2 Day 28) where administered via different routes;
- CAB 200 mg/mL plasma trough concentrations (C_τ) at Week 4 (Injection 1 Day 28) for Cohorts 4h compared to historical CAB 200 mg/mL data (Week 8 C_τ following first injection at Week 4b in ATLAS/FLAIR);
- CAB 400 mg/mL plasma trough concentrations (C_τ) at Week 4 (Injection 1 Day 28) for Cohorts 1, 2, 3, 4, 4b and 4h compared to historical CAB 200 mg/mL data (Week 8 C_τ following first injection at Week 4b in ATLAS/FLAIR);
- CAB 400 mg/mL plasma trough concentrations (C_τ) at Week 8 (Injection 2 Day 28) for Cohorts 1, 2, 3, 4, and 4b compared to historical CAB 200 mg/mL data (Week 12 C_τ following second injection at Week 8 in ATLAS/FLAIR);
- CAB 400 mg/mL plasma trough concentrations (C_τ) at Week 12 (Injection 1 Week 12) for Cohorts 5 and 6 (if conducted) compared to historical CAB 200 mg/mL data (Week 8 C_τ following first injection at Week 4b in ATLAS/FLAIR).

Relative bioavailability assessments using pair-wise comparisons between cohorts in the current study may be done with dose-normalized PK parameters if the doses administered are different in different cohorts.

Following log transformation, PK concentration or PK parameters will be separately analyzed using a linear regression model with fixed effect terms for the treatment. Point estimates and corresponding 90% confidence intervals will be constructed for the differences (CAB 400 mg/mL – CAB 200 mg/mL). The point estimates and their 90%

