2. SUMMARY OF KEY PROTOCOL INFORMATION

2.1. Changes to the Protocol Defined Statistical Analysis Plan

There were no changes or deviations to the originally planned statistical analysis specified through protocol amendment 6.

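### The SAP omits the protocol's primary Injection 2 historical trough comparison for Cohort 4, while its Section 2.1 says nothing changed

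*SAP*

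**What the plan says.** Protocol Section 10.4.2 introduces the geometric mean ratio comparisons as primary: "In addition, the primary analyses will also include the following assessments based on geometric mean ratios". One of its bullets covers the CAB 400 mg/mL trough "at Week 8 (Injection 2 Day 28) for Cohorts 1, 2, 3, 4, and 4b compared to historical CAB 200 mg/mL data", the historical value being the trough after the second ATLAS/FLAIR injection. Protocol Table 4 gives planned Week 8 precision for this ratio for Cohorts 1-4.

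SAP Section 5.1 lists three Injection 2 historical comparisons:

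- First row: "C1 CAB400 - Inj. 2 400 mg IM Gluteal vs Week 4 post injection 2 in ATLAS/FLAIR IM Gluteal CAB 400 mg"
- Second row, with the historical value normalised to the 200 mg level: "C2 CAB400 - Inj. 2 200 mg SC Abdomen vs Week 4 post injection 2 in ATLAS/FLAIR IM Gluteal CAB 400 mg"
- Third and last row: "C3 CAB400 - Inj. 2 400 mg IM Lateral Thigh vs Week 4 post injection 2 in ATLAS/FLAIR IM Gluteal CAB 400 mg"

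Cohort 4 does appear in the Injection 1 list: "C4 CAB400 - Inj. 1 400 mg IM Gluteal vs Week 4 post injection 1 in ATLAS/FLAIR IM Gluteal CAB 600 mg", normalised to 400 mg.

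SAP Section 8.1.5.1 names Cohorts 4 and 4b for the historical comparison without saying which injection, and points to Section 5.1 for what will be run. SAP Section 2.1 states: "There were no changes or deviations to the originally planned statistical analysis specified through protocol amendment 6". The amendment table in SAP Section 1.1 records that the comparison list was updated. It mentions no removal and gives no reason.

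**The concern.** A programmer following the SAP would produce no Injection 2 historical ratio for Cohort 4, although the protocol counts it as primary. A reader relying on SAP Section 2.1 would not know that a protocol comparison is missing.

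Cohort 4 is the only cohort with an intramuscular first injection and a subcutaneous second one. No other row in the Injection 2 list covers that sequence. At stake are the completeness of the primary PK reporting and the accuracy of the SAP's statement on deviations.

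**Working it through.** **1. Compare the cohort lists for the Injection 2 historical comparison.**

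| Cohort | Protocol 10.4.2 | SAP 5.1 |
|---|---|---|
| 1 | yes | yes |
| 2 | yes | yes, normalised to 200 mg |
| 3 | yes | yes |
| 4 | yes | no |
| 4b | yes | not visible |

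The protocol set {1, 2, 3, 4, 4b} less the SAP set {1, 2, 3} leaves {4, 4b}.

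**2. Check whether redaction explains the gaps.**

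- Cohort 4: its Injection 1 row and both of its dose descriptors in SAP Section 5.1 are readable, and the Injection 2 list is numbered 1 to 3 with no redaction mark after item 3. Redaction is not a plausible explanation.
- Cohort 4b: its injection descriptors are blacked out, as is item 5 of the Injection 1 list, which by position is probably its row. Item 5 kept its number and mark, so an unmarked deletion from the Injection 2 list is less likely, but it cannot be excluded.

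**3. Check whether other SAP text restores the comparison.** Section 8.1.5.1 names Cohort 4 but defers to Section 5.1. Its condition that data be sufficient applies when the analysis is run and does not explain a row absent in advance.

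**4. Reproduce the protocol's planning figure.** Inputs from protocol Table 4, Week 8: SD of log concentration 0.47376, n₁ = 15, n₂ = 577, 90% CI. The log half-width is

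h = t(0.95; n₁+n₂−2) × SD × √(1/n₁ + 1/n₂)

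With 590 degrees of freedom, h = 0.20412 (stated 0.20413). At a ratio of 1.0 the interval is exp(±0.20412), or 0.8154 to 1.2265, as in Table 4.

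**5. Precision of the missing rows.**

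- Cohort 4, n = 15: the figure above. Under the unequal-variance model in SAP Section 8.1.5.1, with the same SD in both groups, the degrees of freedom fall to about 14.7 and the interval becomes 0.805 to 1.243.
- Cohort 4b, 18 evaluable, same SD assumed: h = 0.18681, interval 0.830 to 1.205 (pooled).

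**6. Effect of the SAP's normalisation on a Cohort 4 row.** Scaling the historical 400 mg trough in proportion to 200 mg multiplies it by 200/400 = 0.5. The normalised ratio is therefore 1/0.5 = 2 times the unadjusted ratio, with the same log half-width. This corrects for the second dose only, not for the first dose (400 mg against 600 mg) or the route.

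**The case against.** The strongest defence is that the list follows an unstated rule. The historical regimen is 600 mg then 400 mg, both gluteal. Cohorts 1, 2 and 3 were all planned with a 600 mg first injection. Two Cohort 3 participants received 400 mg, and SAP Section 8.1.1.2 adds parameters adjusted to 600 mg for them. The one Injection 2 pairwise row in Section 5.1 is restricted to Cohort 3 participants whose first injection was 600 mg. Cohort 4 had 400 mg gluteal then 200 mg subcutaneous, so its Week 8 trough mixes carry-over from a different first dose with absorption by another route.

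This is a fair reason for caution, and it stands as one. A reader might answer that Cohort 2 has the same difficulty. It does not: it shares the 600 mg first dose and used one route throughout, and only its second dose differs. But the SAP never states such a rule. Protocol Amendment 6 kept Cohort 4 in this comparison even though its regimen had been agreed on 22 December 2020 and is set out in the same document. The argument could justify a declared deviation, but not an undeclared one.

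It is also true that little is lost. Cohort 4's Injection 2 trough and its dose-normalised version are derived and summarised with geometric means and 95% CIs (SAP Sections 8.1.1.2 and 8.1.2). Its Injection 1 historical comparison remains. No hypothesis is tested, so neither error rates nor power are affected.

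**Conclusion.** The point holds for Cohort 4. One of the protocol's five primary Injection 2 historical comparisons is omitted without explanation, and SAP Section 2.1 is incorrect as it stands. For Cohort 4b, the visible text is consistent with an omission but does not establish one, so at most two of five are affected.

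A reader might infer that a result was dropped selectively once the sponsor had seen the data. The documents do not support this. The previous SAP's list and the date of the SAP amendment are not available, so it cannot be shown that a Cohort 4 row ever existed and was removed. The study is sponsor-unblinded by design, so access to data is no evidence of motive.

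The precision figures assume that the ATLAS/FLAIR Week 8 SD applies to Cohort 4. That SD comes from gluteal dosing at 600 mg then 400 mg, so the interval is indicative only. It describes how well the missing ratio would be estimated and does not measure harm. This is a documentation and completeness fault that should be corrected.

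**What to change.** - Add a Cohort 4 Injection 2 row to the historical list in SAP Section 5.1 and to Table 3.6. Normalise it to 200 mg as in the Cohort 2 row, and label it with the full sequence (400 mg IM gluteal, then 200 mg SC abdomen). The unadjusted ratio may be shown alongside.
- Confirm that the unredacted SAP contains a Cohort 4b Injection 2 row, and add one if it does not.
- If either comparison is deliberately not run, for example because the first dose and route differ from the historical regimen, correct SAP Section 2.1 to record the deviation, its reason, and its date relative to data review.

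The cost is one or two table rows, or one paragraph, and no new data. The downside is that the added ratios need a footnote, because normalising for the second dose does not remove the difference in first dose or route.
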